Mindfulness is a promising emotional regulation skill that could reduce negative biases in emotion perception. Identifying a brief intervention that effectively reduces negative emotions is necessary to investigate the impact of emotion regulation on emotion perception. Previous research has shown that mindfulness is a skill that is positively associated with both emotion perception ability and emotion regulation (Quaglia, Goodman, & Brown, 2015). First, mindfulness can be used to modulate experiences of negative emotions (Chambers, Gullone, & Allen, 2009; Roemer, Williston, & Rollins, 2015). For example, one study found that a 15-minute mindful breathing induction led to less negative emotional responses to negatively-valenced stimuli than control condition (a worry induction) (Arch & Craske, 2006a). Secondly, brief mindful breathing interventions can also lead to improvements in emotion perception. (Tan, Lo, & Macrae, 2014) Taken together, findings suggest that mindful breathing can be used as an emotion regulation skill that may have beneficial impacts on emotion perception. To our knowledge, these relationships have yet to be tested within clinical samples with emotion dysregulation. Given its established effect on emotion regulation, a mindful breathing skill will be taught to participants as an emotion regulation skill as a micro-intervention. A useful comparison condition would be a micro-intervention that targets perspective-taking (Jackson, Meltzoff, & Decety, 2005), another social cognitive process related to perceiving other people's emotions. Perspective-taking inductions may share similar mechanisms as mindfulness as another type of metacognitive intervention, but they do not address dysregulated emotions. Therefore, a perspective-taking micro-intervention will be used in this study as the active comparison condition.

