## Measures and Tasks

Interviews: During the intake session, diagnostic exclusions and current/past prevalence of Axis I and II diagnoses will be determined by the Structured Clinical Interview for Mental Disorders-I and II (SCID-I and II for DSM-5), interviews with demonstrated reliability used in our lab. The Treatment History Interview, brief version (B-THI; Linehan & Heard, 1987) will also be used at the intake session to assess previous and ongoing psychiatric services received and the NART will assess reading ability. All interviews will be videotaped or audio recorded and [name] will determine the reliability of every tenth interview. These video and/or audio recordings will be recorded directly onto the assessor's Duke computer, using a USB connected web camera that is connected to the hard drive of that computer. The recordings do contain PHI and thus the Duke lab computer used for recording has been encrypted with PGP. These video/audio files will be only temporarily stored on the local Duke computer and will be moved to Department of Psychiatry & Behavioral Sciences protected folder.

If the participant recently took part in another study at CBRTTP, he or she may not be required to complete all portions of the SCID interviews. Specifically, if the participant completed a SCID-I diagnostic interview with one of our study assessors within the previous four weeks, he or she would only be required to complete any portions of the SCID-I not completed as part of the earlier study assessment. If the participant completed the SCID-II within the previous six months, he or she would not be required to complete the SCID-II. In those cases, data from the earlier assessments would be used for this study. These procedures reduce the burden on the participant by eliminating the need to duplicate lengthy interviews, while still ensuring that the data is current.

Emotion Perception: The main outcome measure of emotion perception will be assessed with behavioral tasks, described below.

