Face-reader data collection. We have acquired new software (Facereader from Noldus) that can be used to analyze facial expressions from an inputted video and to output emotional experiences resultant from the facial analysis. This software complements the physiological data acquisition that we are doing and can add a new dimension to our data collection and analysis. We plan to video record participant's faces during the stressor and regulation periods of the study using a Microsoft webcam that is connected directly to a Duke approved laptop or computer. We will ask at consent for special permission for this procedure. We will only record participants' faces if consent is given. These recordings will be transferred right away at the end of the session on a secured server and deleted from the laptop (similar procedures as for assessment videos). The videos will be kept up to 6 years post study finish and deleted within that timeframe.

Psychological Functioning: Exploratory outcome variables will be changes in self-reported impairments in daily functioning and other psychiatric symptoms. These include:

1. Difficulties in Emotion Regulation Scale (DERS) (Gratz, 2004)
2. Interpersonal Reactivity Index (IRI),(Davis, 1980)
3. Toronto Mindfulness Scale (TMS) (Lau, et al., 2006),

4. Basic Empathy Scale (BES) (Carre et al., 2013)
5. Patient Health Questionnaire-depression module (PHQ-9) (Kroenke & Spitzer, 2002)
6. Social Interaction Anxiety Scale (SIAS; Mattick & Clarke, 1998)
7. NIH Toolbox Adult Social Relationship Scales (NIH SRS) (Cyranski, 2013)
8. Ambiguous Intentions Hostility Questionnaire (AIHQ-A; Combs et al, 2007)
9. Early Memories Task (EMT; Mayman, 1968)
10. Psychological Flexibility Questionnaire (PFQ; Ben-Itzhak, 2014))

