#### Experimental Procedures

Intake Session: After determining eligibility, participants will complete measures of social and psychological functioning (DERS, IRI, PANAS-2, TMS, AIHQ-A, NIH SRS, PHQ-9, BES, EMT, SIAS, PFQ) and the two laboratory emotion perception tasks (BLERT, EPBT) through an online Qualtrics survey on a standard desktop computer in the laboratory. At this time, they will provide four recent stressful experiences for the personalized stressor task.

Training Session: All participants will come back to their lab for this session (ideally between 5-7 days after the intake session), which will take approximately 1.5 hours. First, all participants will be asked about: 1) current distress and suicidal urges (i.e. Suicide Risk Protocol), 2) any changes in medications since the previous visit, 3) nicotine, caffeine, and alcohol use that day, 4) subjective units of general psychological distress (SUDS; visual analogue scale from 1-9), 5) dissociation state, assessed using self-report (Dissociative-Tension States Scale 4 item version-DSS-4 from the DSS-acute), 6) levels of arousal with the Sedation Scale, and 7) current affect with the PANAS-2. Then, the experimenter will affix electrodes and will use Biopac MP150 hardware and AcKnowledge software for data acquisition. All participants will be assessed for baseline negative emotional arousal with psychophysiological (galvanic skin response) measures for five minutes. Then, participants will be randomized to one of three groups:

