## Selection of Subjects

Inclusion criteria include

- (1) ages 18-55;
- (2) have a smartphone and agree to receive text-messages;
- (3) high emotion dysregulation, assessed with the Difficulties with Emotion Regulation Scale (DERS)(Gratz & Roemer, 2004). There is no single consensus definition of difficulties with emotion regulation. However, one influential contemporary model proposes a multi-dimensional approach to conceptualizing difficulties with emotion regulation, including difficulties with: emotional awareness, emotional clarity, achieving goals when upset, impulsivity when upset, unwillingness to accept negative affect when upset, and accessing strategies to regulate emotions when upset (Gratz & Roemer, 2004). In the present application, we utilize this model and accompanying measure, the Difficulties with Emotion Regulation Scale (DERS; Gratz & Roemer), when characterizing our sample as being individuals who have problems regulating emotions. The mean DERS total score across all published reports (n = 13) with adult psychiatric samples (n = 19) is 112.15 (SD = 22.38). Following the established protocols from previous studies, we will use a total score of 90 or higher in the DERS for inclusion. In our previous study (Pro000035922), the 208 eligible participants had a mean DERS score of 117.6 (SD=17.95) at intake. These participants met criteria for a variety of affective and personality disorders, including major depression (68.3%, 22.1% current), generalized anxiety disorder (40.4%), and borderline personality disorder (11.1%). Therefore, we are confident that this DERS threshold will ensure recruitment of a transdiagnostic, clinical sample with emotion dysregulation.

Exclusion criteria include

- (1) Current mania;
- (2) Meets criteria for any current psychotic disorder symptom;
- (3) Currently/chronically homeless;
- (4) Current suicidal ideation (see data & safety section for specific criteria);
- (5) Psychiatric hospitalization within past 6 months;

(6) Unable to read, blind or deaf. Our previous study recruited only participants who were currently in treatment, but this study will include both participants who are currently in treatment, as well as those who are not in treatment. Intelligence Quotient (IQ) will be assessed with the North American Adult Reading Test (NART). 21-22 Subjects with a NART calculated IQ score of <90 will be excluded from the study.

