## Data Analysis & Statistical Considerations

For the primary outcome of biases in emotion perception, the estimates were derived from a mean difference between conditions. With a Type-I error rate of 5% and 72 participants (24 per group), we will have at least 80% power to detect a medium to large effect size (Cohen's  $f = 0.38$ ), based on previous research demonstrating negative biases in emotion perception using similar behavioral measures. (Schmid & Schmid Mast, 2010) Because we anticipate a 10% to 15% rate of dropout, 30 participants will be randomized to each group. Therefore, this study will recruit 90 adult participants over the age of 18 who have high emotion dysregulation and interpersonal problems.

Since 2004, the CBTRP has recruited a range of adult psychiatric samples all characterized by problems with emotion regulation. Across studies of emotional functioning, it is estimated that our lab has run over 980 participants since 2004, at a rate of roughly 90 per year. In our previous NIMH project, over 33 months we have screened 1154 individuals and enrolled 169 participants, at a rate of 5.12 per month. We project enrolling 90 participants over 14 months, at a rate of 6.43 per month. Given our demonstrated track record of success meeting the required recruitment target in the present application, we expect to meet recruitment targets in the proposed project.

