Specific Aim 1: Aim 1 will determine if the emotion regulation intervention leads to fewer negative biases in emotion perception during the laboratory training session. For this aim, we will conduct ANCOVA analyses to study group differences in performance on the emotion perception laboratory tasks, controlling for their baseline scores assessed in the intake session. To compare the conditions' impacts on negative biases, we will analyze group differences in 1) number of trials with neutral facial expressions are misclassified as negative emotions; 2) accuracy for positive emotions and negative emotional expressions. We will also examine the relationship between emotional distress and emotion perception. Hypothesis 1: Participants in our emotion regulation condition will have less negative bias in emotion perception (e.g. fewer neutral faces misclassified as negative, lower accuracy for negative emotions, higher accuracy for positive emotions) compared to participants in both the control conditions. Even though the perspective-taking and mindful breathing conditions may have similar effects (e.g. increasing attention to social cues (Olsson et al., 2016; Quaglia, Goodman, & Brown, 2016)), perspective-taking inductions may still lead to mood-congruent biases by increasing negative emotional responses (Lamm, Batson, & Decety, 2007). Therefore, we predict that the emotion regulation intervention would reduce this bias significantly more than both the worry and perspective-taking conditions. We also predict that intensity of emotional distress will be related to negative biases in emotion perception.

Specific Aim 2: Aim 2 will compare the changes in emotion perception over time between the emotion regulation breathing condition and the control conditions. For this aim, Multilevel modeling (MLM) will be used because it permits evaluation of longitudinal data on participants over time with trajectories for each participant examined as random effects. We will conduct MLM analyses to study group differences in changes in the laboratory emotion perception tasks assessed during intake (time 1), the training session (time 2) and after the testing phase (time 3). For the phone-based behavioral task, we will first examine the psychometric properties of this measure in this clinical sample. Then, we will analyze group

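### Current treatment and intake mindfulness are collected but named as covariates in neither the Aim 1 nor the Aim 2 analysis, which forgoes some precision and leaves chance imbalance unadjusted

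*Combined protocol and SAP*

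**What the plan says.** - **Population.** Selection of Subjects (exclusion criterion 6) notes that the previous study enrolled only people in treatment, whereas "this study will include both participants who are currently in treatment, as well as those who are not in treatment". Everyone must score 90 or higher on the DERS.
- **What is collected.** Under Measures and Tasks (Interviews), the brief Treatment History Interview "will also be used at the intake session to assess previous and ongoing psychiatric services received". Under Experimental Procedures (Intake Session), participants "complete measures of social and psychological functioning (DERS, IRI, PANAS-2, TMS, AIHQ-A, NIH SRS, PHQ-9, BES, EMT, SIAS, PFQ"; the list includes the TMS. Randomisation comes later, at the training session.
- **Why it could matter.** Background & Significance says that "mindfulness is a skill that is positively associated with both emotion perception ability and emotion regulation".
- **What the analysis uses.** In Data Analysis & Statistical Considerations, the Aim 1 ANCOVA compares groups "controlling for their baseline scores assessed in the intake session", and no other covariate is named. The Aim 2 multilevel model covers intake, training session and end of the testing phase, and mentions neither treatment status nor TMS. No randomisation method or stratification factor is described.
- **Timing.** The Clinical Assessment paragraph under Selection of Subjects allows interview portions and self-report scales that do not bear on eligibility to be finished on a later day, including after the computer experiment on Day 1.

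**The concern.** The protocol itself says that mindfulness goes with emotion perception, which is the construct behind the primary outcome. It measures mindfulness at intake and then leaves it out of the model. It also widens entry to a mix of treated and untreated people, records who is in treatment, and makes no stated use of that in the confirmatory analyses. With 24 to 30 people per arm, a baseline characteristic can differ noticeably between arms by chance. A prognostic covariate both corrects for such a difference and reduces residual variance. The calculated power is only just above 80%, so a gain at almost no cost is worth taking.

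**Working it through.** **Inputs from the plan.** "With a Type-I error rate of 5% and 72 participants (24 per group), we will have at least 80% power", at Cohen's f = 0.38. "Because we anticipate a 10% to 15% rate of dropout, 30 participants will be randomized to each group". The plan gives no share in treatment, no effect of treatment status on the outcome and no correlation of TMS with it. All of these are assumptions below, shown as ranges.

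**Step 1: the plan's own figure.** I assume an omnibus F test with three groups and numerator df 2, noncentrality λ = N·f² = 72 × 0.38² = 10.40.
- No covariate, denominator df 72 − 3 = 69: power 81.3%.
- Baseline score as covariate, df 68: power 81.3%.

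The stated power of at least 80% is reproduced.

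**Step 2: adding the two covariates.** Each takes 1 df, so the denominator df is 72 − 3 − 3 = 66. I take f = 0.38 as relative to the residual SD after baseline adjustment, which the plan does not specify. If the covariates explain a further share R² of residual variance, f′ = f/√(1 − R²) and λ′ = 72·f′².

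| Assumed R² | f′ | λ′ | Power |
|---|---|---|---|
| 0 | 0.380 | 10.40 | 81.3% |
| 5% | 0.390 | 10.94 | 83.3% |
| 10% | 0.401 | 11.55 | 85.4% |
| 15% | 0.412 | 12.23 | 87.4% |

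The gain is 2 to 6 points. At R² = 0 power moves from 81.32% to 81.26%, a loss of less than 0.1 point.

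**Step 3: chance imbalance.** I assume simple randomisation with independent binomial counts in two given arms, and compute the exact probability that the shares in treatment differ by at least 20 percentage points. That means 5 or more people at 24 per arm (0.20 × 24 = 4.8) and 6 or more at 30 per arm.

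| Assumed share in treatment | 24 per arm | 30 per arm |
|---|---|---|
| 30% | 15.5% | 12.0% |
| 50% | 19.3% | 15.5% |

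**Step 4: what such an imbalance does.** If treatment status shifts the outcome by an assumed 0.2 to 0.5 SD, a 20-point imbalance moves a contrast by 0.20 × 0.2 = 0.04 SD to 0.20 × 0.5 = 0.10 SD. The planned effect, if the two comparison arms have equal means, is d = f × 3/√2 = 0.38 × 2.121 = 0.81. In 10,000 simulated null trials (N = 72, half in treatment, 0.5 SD effect of treatment status, unadjusted analysis) the type I error was 4.8%.

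**Step 5: a treatment-by-arm interaction.** Take half the sample in treatment, d = 0.81 in the untreated, equal comparison arms, a 2-df test and N = 72. Power is about 27% if treatment abolishes the effect and about 10% if it halves it.

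**The case against.** Randomisation balances prior treatment and mindfulness in expectation, and the unadjusted test keeps its level. The likely shift from an imbalance is small beside the planned effect, and the baseline task score may already absorb part of it. The Background's statement concerns mindfulness and says nothing about current treatment, so only TMS is prognostic by the protocol's own account. All of this stands, and it limits the point to precision and chance imbalance.

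The timing allowance also cuts against a careless fix. Neither the treatment history interview nor the TMS is an eligibility item. If Day 1 of the experiment means the training session, some participants could complete the TMS after being taught mindful breathing, and adjusting for such a value could bias the contrast. The covariates are sound only if recorded before randomisation.

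A reader might go further and infer that comparison participants who already have regulation skills dilute the contrast, or that the arms are systematically unbalanced. The documents do not support either reading:
- They give no share in treatment, type of therapy or size of effect, and being in treatment is not the same as having the skill.
- The DERS floor restricts how skilled entrants can be.
- The previous study enrolled only treated people and still reported effects on distress, although with habituation as the technique and a different outcome.
- If the effect were truly smaller in people who already have the skill, covariates or stratification would not restore it.

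Nor does the plan say that randomisation is unstratified; it is silent. The moderators named for use if the hypotheses fail are open-ended examples, not a closed list.

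**Conclusion.** The omission is real and minor. Two baseline variables that the trial already collects, one of them linked to emotion perception by the protocol itself, are named in neither the Aim 1 nor the Aim 2 analysis. Validity is not at stake. What is lost is up to about 6 points of power at N = 72, and protection against imbalances of 20 points or more that arise between two given arms in roughly one randomisation in five to one in eight. The power gain rests on the assumed 5% to 15% of residual variance, and the imbalance figures on the assumed 30% to 50% in treatment and on simple randomisation. The gain was calculated for the Aim 1 comparison only.

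**What to change.** - Prespecify current treatment (yes/no, from the Treatment History Interview) and intake TMS as covariates in the Aim 1 ANCOVA, alongside the baseline task score, and in the Aim 2 multilevel model. Intake is itself the first time point in Aim 2, so the plan should state whether the covariates enter as main effects only or also by time.
- Require the treatment-status item and the TMS to be completed before randomisation, and exclude them from the allowance to finish items after the experiment.
- Stratifying randomisation by current treatment is optional.
- Label any treatment-by-arm analysis exploratory, because its power is low.

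Cost: two degrees of freedom in the ANCOVA (under 0.1 point of power), a few lines of analysis text and a small scheduling constraint at intake. No new measures are needed.

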(7) high self-reported autistic traits, as assessed by the Autism Spectrum Quotient (Auyeung & Baron-Cohen, 2012). If participants score more than 6 out of 10 for the total score, they are considered at risk for autism.

**Clinical Assessment.** Individuals not excluded by the phone screen will come to the lab to determine eligibility for the study. Upon arrival, a Clinical Assessor will review the consent form, answer any questions, and obtain written informed consent. Next, the Clinical Assessor will administer diagnostic interviews (SCID I, II for DSM-5) and self-report instruments (i.e., demographics, DERS) needed to assess all other inclusion/exclusion criteria. Ineligible participants will be debriefed and compensated (\$10) for their partial participation. Eligible participants will complete remaining assessments. This approach helps to reduce unnecessary participant burden and increase project efficiency. After inclusion/exclusion criteria are assessed and eligibility is confirmed, participants will schedule their next appointment (ideally min 1 day and max 14 days post screening). Of note, the population being seen in this study can have many different problems currently and in their past and sometimes the interview assessments, along with assessing inclusion/exclusion criteria, can last longer than expected. At the subject's discretion, we may have to finish portions of the assessment interviews (non inclusion/exclusion portions) on a second day. If that is the case, the subject will finish the interviews or the self-report scales on a separate day or on Day 1 of the experiment, after the computer experiment.

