differences in the valence of emotion perception ratings over the one-week testing phase. We will also examine whether changes in emotion dysregulation and distress mediate changes in negative biases over time. Finally, we will also explore the effects of the intervention on self-reported psychological and social functioning. Hypothesis 2: One week of hearing the tones via mobile phones will lead to greater long-term changes in negative biases emotion perception for participants in the emotion regulation condition compared to the participants in the control conditions. Changes in emotional regulation and distress over time will mediate changes in negative biases in emotion perception over time.

If our hypotheses are not supported and the conditions do not have significantly different effects on emotion perception, these findings would be indicative of trait-like deficits in emotion perception beyond the momentary effects of mood or perspective-taking. We would then use moderation analyses to explore the role of other stable factors within emotion perception performance, such as trait empathy (measured by the IRI) or psychiatric diagnoses.

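### Unfinished intake scales and non-eligibility interview parts may be completed after randomisation and the assigned condition, and no rule keeps those values out of the baseline

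*Combined protocol and SAP*

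**What the plan says.** Experimental Procedures (Intake Session) places the self-report battery at intake: "participants will complete measures of social and psychological functioning (DERS, IRI, PANAS-2, TMS, AIHQ-A, NIH SRS, PHQ-9, BES, EMT, SIAS, PFQ"). It also places there "the two laboratory emotion perception tasks (BLERT, EPBT) through an online Qualtrics survey". The Training Session text begins with state measures and a five-minute skin-conductance baseline. It continues "Then, participants will be randomized to one of three groups", and the stressor task under the assigned condition follows.

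Selection of Subjects (Clinical Assessment) adds an exception for long intakes. Staff may have to "finish portions of the assessment interviews (non inclusion/exclusion portions) on a second day", and in that case the participant may "finish the interviews or the self-report scales on a separate day or on Day 1 of the experiment, after the computer experiment". The same section gives first the "self-report instruments (i.e., demographics, DERS) needed to assess all other inclusion/exclusion criteria".

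On use of the data, Measures and Tasks says "Exploratory outcome variables will be changes in self-reported impairments in daily functioning and other psychiatric symptoms". Data Analysis & Statistical Considerations adds that, if the hypotheses are not supported, moderation analyses will explore stable factors "such as trait empathy (measured by the IRI) or psychiatric diagnoses".

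**The concern.** A baseline has to be taken before anything that differs between arms. The exception lets some nominal intake values be collected after participants have been allocated and have gone through mindful breathing, habituation or the uninstructed stressor task. Two uses of the data are exposed.

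- **Change outcomes.** If the recorded starting value already contains part of an arm's effect, subtracting it removes that part from the estimate.
- **Moderators.** An IRI score or diagnosis recorded after treatment can itself be influenced by treatment, and an interview can be rated by someone who knows the arm. The documents describe no blinding of the assessor.

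The plan does not ask for late values to be dated, flagged or kept out of the baseline.

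**Working it through.** **Step 1: what Day 1 means.** Study Overview gives two lab sessions, intake and training, followed by a week of phone prompts. The exception concerns a day after the assessment day. The only such lab day is the training session, and its experimental task comes after randomisation. Neither Day 1 nor the computer experiment is defined, so this is the natural reading and not a certain one.

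**Step 2: which items are exposed.**

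- *Exposed:* of the ten measures listed under Psychological Functioning, the nine other than DERS (IRI, TMS, BES, PHQ-9, SIAS, NIH SRS, AIHQ-A, EMT, PFQ), and the interview portions not needed for eligibility.
- *Exposed, with a fallback:* the intake PANAS-2. As a measure of current state it could easily move, but it is repeated at the start of the training session before randomisation.
- *Not shown to be exposed:* DERS, demographics and the eligibility parts of the interviews, which are completed to establish eligibility. The same holds for BLERT and EPBT. The exception names only interviews and self-report scales, and Specific Aim 1 defines the ANCOVA covariate as the intake score.

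**Step 3: possible size.** The plan's only related figure is its power statement, which is not in dispute. With N = 72 and f = 0.38, the noncentrality is 72 × 0.38² = 10.40. The three-group F test at 5% (2 and 69 df) then has 81.3% power, consistent with the stated 80% or more.

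The documents give neither a deferral rate nor a shift size, so the rest is illustration. Let δ be the true arm effect, q the share of late baselines, and s the fraction of δ that a late baseline already carries. The active arm's recorded baseline mean is then too high by q·s·δ, which gives:

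- change-score contrast = δ − q·s·δ = (1 − q·s)·δ
- baseline-adjusted contrast ≈ (1 − r·q·s)·δ, where r is the baseline-to-outcome correlation

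| Assumed q | Change score, s = 1 | Change score, s = 0.5 | Adjusted, r = 0.5, s = 1 | Adjusted, r = 0.7, s = 1 |
|---|---|---|---|---|
| 10% | 90% | 95% | 95% | 93% |
| 20% | 80% | 90% | 90% | 86% |
| 30% | 70% | 85% | 85% | 79% |

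A simulation (two arms of 24, 4,000 runs, s = 1, δ = 0.8 SD) gave 95.9%, 90.8% and 85.8% for r = 0.5, and 92.9%, 86.1% and 80.5% for r = 0.7. These are within 1.5 percentage points of the formula. With 24 per group, 10% to 30% is about 2 to 7 participants per arm.

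**The case against.** The case for treating this as minor has four parts.

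- **Frequency.** The rule is permissive. It applies when intake overruns, is at the participant's discretion, and offers a separate day first. This stands: the text shows that late values can occur, not that they will or how often.
- **Importance.** The self-report changes are labelled exploratory, and the moderation analyses run only if the hypotheses are not supported. This also stands and limits the priority.
- **Shared exposure.** Deferred participants in every arm would answer after the stressor task, so part of any shift is common and cancels between arms if deferral is similar across them. That is correct for the common part. The arm-specific part does not cancel, and it is what the study is designed to detect.
- **Size.** A large shift is implausible for trait measures such as the IRI, or for diagnoses, after one session of about 1.5 hours. This stands for those measures. It is weaker for the TMS, because one arm has just been trained in mindful breathing. Even so, the TMS would not come directly after the training: the post-stressor ratings, the bias task and the manipulation check are scheduled first.

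A reader might also infer that the main Aim 1 comparison or the DERS is contaminated. The documents do not support this, for the reasons in Step 2 of the working.

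**Conclusion.** The point holds as a gap in the baseline rule for exploratory and conditional analyses. A stated provision, on its natural reading, allows baseline scales and non-eligibility interview parts to be collected after randomisation and exposure. The plan names no other baseline for the exploratory change outcomes or the IRI and diagnosis moderators, and nothing excludes late values.

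Under the least favourable assumption (late values carry the full arm effect, raw change scores), a contrast keeps 90% to 70% of its true size for an assumed 10% to 30% late. Baseline adjustment, a partial carry-over or a stable trait measure all reduce the loss. A bias in SD units cannot be derived, because the documents give no shift size. That late values would be filed as baseline is an inference from the plan's silence and should be confirmed with the sponsor, as should the meaning of Day 1. The sample size is unaffected. The change is worth making because it is cheap and the resulting bias could not be detected afterwards without completion dates.

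**What to change.** In Selection of Subjects (Clinical Assessment), delete the Day 1 alternative. Require outstanding scales and interview portions to be finished on a separate day before the training session. The scales already run in Qualtrics and can be completed online, and the section's own scheduling window (ideally 1 to 14 days after screening) leaves room.

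Do not move this work to the start of the training visit. Risk/Benefit Assessment says that interviews and questionnaires can be stressful, and the skin-conductance baseline taken at that visit is the reference for tone delivery.

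Add to Data Analysis & Statistical Considerations that completion dates are recorded. State there that any scale or interview item completed after randomisation is treated as missing for baseline, change-score and moderator use. Because BLERT and EPBT share the intake survey with the scales, also state that they cannot be deferred.

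The cost is a few sentences in an amendment, a short extra contact for some participants, and a few missing exploratory baselines.
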